5.1.2. Secondary Study Endpoints

The secondary endpoint will be number of tacrolimus or Envarsus XR dose adjustments required during the period of DGF.

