Total 100 patients: Obtain informed consent. Screen potential subjects by inclusion and exclusion criteria, review labs and documentation. All patients will have received or will be receiving immediate release tacrolimus as standard of care (SOC)

Visit 1 (Diagnosis of DGF)

Perform baseline assessments.
Medical records and the Transplant Database will be reviewed for the following: Routine blood test, urine test and other radiological investigation based on the clinical judgment. Commonly used test include: CBC, Lyses, BUN, Creatinine, glucose, urinalysis, urine protein/creatinine, immunosuppressive level

Visit 2 (Diagnosis of DGF)

Randomize into Tacrolimus (SOC) or Envarsus XR (study) group

Visit 3 (Daily while inpatient
Or in clinic visit)

Medical records and the Transplant Database will be reviewed for the following: Follow up assessments of study endpoints and safety.
Evaluate for need of dialysis or not. Review routine blood test performed in the morning along with urine output in last 24 hours and examinations to assess the

Visit 4 (recovery from DGF)

Medical records and the Transplant Database will be reviewed for study endpoints and safety, Routine blood test performed, H&P documenting discharged from the DGF clinic

Visit X (Time Point)

Medical records and the Transplant Database will be reviewed for the following:
Interval between transplants to the recovery of DGF
Interval between first and last dialysis
Total number of dialysis
Total number of tacrolimus or Envarsus XR dose adjustment required

2. Key Roles

2.1. *Investigator and Study Center:*

[name], MBBS
Assistant Professor (CHS)
Department of Medicine-Nephrology
[name]
[name]
[name]
[name]
[contact]
Email: [contact]

Principal Investigator:

University of Wisconsin Hospital and Clinics
[name]
[name]

Participating sites:

UW Health-University of Wisconsin Hospital and Clinics
Clinical Laboratories
[name]
[name]

Local Laboratory Services:

[name]
[name]
School of Medicine and Public Health
[name]
Email: [contact]

**ICTR Data Monitoring
Committee Contact:**

[name]
School of Medicine and Public Health
[name]
Ph: [contact]

**ICTR Study Monitoring
Service Contact:**

Veloxis Pharmaceuticals, Inc
[name],
[name]
[contact]

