3.2. Hypothesis

With extended release Envarsus XR, designed to deliver tacrolimus more consistently, it is hypothesized that there will be less fluctuation of tacrolimus levels requiring less dose adjustment and ultimately early recovery of the DGF.

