5.1.1. Primary Study Endpoints

The primary endpoint of the study will be the interval between first dialysis and last dialysis after kidney transplant (duration of DGF).

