5.1.3. Primary Safety Endpoints

Primary safety endpoints include: infections, malignancies, hematological complications including leukopenia, anemia, and thrombocytopenia, cardiovascular complications and events, neuropathy, tremors, gastrointestinal symptoms, uncontrolled hypertension, serious electrolytes abnormalities and immunosuppression-related adverse effects.

6. Study Subjects – Enrollment and Withdrawal

- A total of 100 subjects (50 subjects in each arm) with the diagnosis of DGF will be enrolled over a period of 2 years.
- DGF is defined as the need for a dialysis within the first week of transplant. Once potential DGF patients are identified, the transplant nephrology team will be consulted and the transplant nephrology provider will perform initial evaluation of a patient, discussion with the patient about his/her interest in participating in the research study and inform the research coordinator.
- Subjects will participate in the study until the recovery of DGF as documented by the provider as “discharged from the DGF clinic” or no need for dialysis for more than one week (7 days).
- Subject would be followed for maximum of 3 months. If they still need dialysis beyond 3 months, will be declared as primary dysfunction and will disqualify from the study.

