9.1. Sample Size Determination

Goal is to analyze 100 subjects total (50 in each group), with a goal to decrease DGF duration to less than 10 days in Envarsus XR group from current mean of 13.9 +/- 7 days with tacrolimus based on the power calculation.

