9.2. Statistical Methods

Continuous data will be compared using Student's t-test or the Wilcoxon Rank Sum test, as appropriate, while categorical data will be analyzed using Fisher's exact test or chi-square test. P values < 0.05 will be considered statistically significant. Kaplan-Meier analyses will be performed to study graft survival if appropriate.

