9.3. Subject Population(s) for Analysis

All randomized and completed study patient data will be used for primary and secondary analysis. Primary analysis include needs for dose adjustment of the Envarsus XR or tacrolimus and secondary analysis include duration of recovery from the DGF.

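### The dose-adjustment total is counted over the DGF period, whose length is the primary outcome, so a lower Envarsus XR count cannot by itself show steadier levels; no endpoint uses the troughs

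*Combined protocol and SAP*

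**What the plan says.** Figure 1 (Visit X) lists the count as "Total number of tacrolimus or Envarsus XR dose adjustment required", and Section 5.1.2 ties it to a period: "The secondary endpoint will be number of tacrolimus or Envarsus XR dose adjustments required during the period of DGF". The primary endpoint in Section 5.1.1 is "the interval between first dialysis and last dialysis after kidney transplant (duration of DGF". Section 9.1 plans to "decrease DGF duration to less than 10 days in Envarsus XR group from current mean of 13.9 +/- 7 days with tacrolimus". For continuous data Section 9.2 offers Student's "t-test or the Wilcoxon Rank Sum test, as appropriate". It names no rate, offset or common counting window.

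The hypothesis in Section 3.2 is that "there will be less fluctuation of tacrolimus levels requiring less dose adjustment and ultimately early recovery of the DGF", and the secondary objective in Section 4 is to reach steady tacrolimus levels. Troughs are drawn for care in both arms (Sections 7.1 and 8.1). No endpoint in Figure 1 or Sections 5.1.1 to 5.1.3, and no analysis in Sections 9.2 or 9.3, uses them.

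Section 9.3 gives the roles the other way round: "Primary analysis include needs for dose adjustment of the Envarsus XR or tacrolimus and secondary analysis include duration of recovery from the DGF".

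On follow-up, Section 6 says "Subjects will participate in the study until the recovery of DGF", and Section 8.2.3 takes patients off study at recovery. Table 1 in Section 8.1, the chart-review table in Section 8.2.1 and the close of Section 8.2.3 speak of visits or participation up to 3 months.

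**The concern.** The count accrues only while DGF lasts, and the trial expects DGF to be shorter on Envarsus XR. A patient with fewer days of DGF has fewer days on which a dose can be changed. Two patients whose levels are equally stable, and whose doses are managed in the same way, can then be expected to differ in their totals. A lower total on Envarsus XR is what the hypothesis predicts through steadier levels, and it is also what shorter DGF can produce without them. The endpoint cannot tell the two apart.

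The levels themselves would speak to the question directly, but nothing in the plan analyses them. The secondary objective would then be left unanswered, or answered from a count that does not measure it.

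**Working it through.** **Inputs from the documents.** Control mean 13.9 days, SD 7 (reading the +/- 7 as an SD); Envarsus XR target 10 days (Section 9.1 says less than 10); 50 per arm; significance level 0.05 (Section 9.2, taken as two-sided).

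**Inputs assumed.** The documents give neither the adjustment rate nor its timing. Assumed: 0.1 to 0.5 adjustments per day, the same behaviour in both arms, gamma-distributed durations (SD 7 in both arms unless stated), Poisson counts.

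**1. The plan's own figure.** n per arm = 2 × (1.960 + 0.842)² × 7² / 3.9² = 50.6, so 51 for 80% power. With 50 per arm, 3.9 / (7 × √(2/50)) = 2.79 and 2.79 − 1.96 = 0.83, which is 79.6% power. The stated 50 is consistent with an unstated 80% power, so 13.9 against 10 days is a fair reading of the planned effect.

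**2. Expected count ratio at identical behaviour.** With even timing, expected count = rate × mean duration, so the rate cancels.
- Full effect, counted to last dialysis: 10 / 13.9 = 0.72. At 0.1 per day that is 1.39 against 1.00 adjustments; at 0.5 per day, 6.95 against 5.00.
- Half effect: mean 13.9 − 3.9/2 = 11.95; 11.95 / 13.9 = 0.86.
- Full effect, counted to recovery (last dialysis + 7 days assumed): 17 / 20.9 = 0.81.
- Equal durations: 1.00.

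**3. How often the raw-count Wilcoxon test rejects** (simulated trials, 50 per arm; ranges run over 0.1 to 0.5 per day):

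| Scenario | Count ratio | Rejects |
|---|---|---|
| Even timing, full effect, to last dialysis | 0.72 | about 35–73% |
| Even timing, half effect | 0.86 | about 13–24% |
| Even timing, full effect, to recovery | 0.81 | 25–61% |
| Clustered early (time constant 14 to 3 days), to last dialysis | 0.78–0.90 | 9–65% |
| Clustered early, to recovery | 0.89–0.99 | 5–32% |
| Equal DGF length | 1.00 | about 5% |

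Repeat runs move these by a point or two (the lower end at half effect came out at 11 to 13%). In the first row, the t-test gives 32 to 63%, an Envarsus XR SD of 5.04 gives a Wilcoxon range of 31 to 66%, and between-patient variation in the rate (gamma variance 0.3) gives 29 to 54%.

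**4. Overlap with the primary endpoint.** At the full effect, about 98% of the significant counts occur in trials where DGF duration is also significant by Wilcoxon. At half the effect the overlap is looser, about 70 to 80% in the same simulation.

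**5. Candidate repairs, with identical behaviour in both arms.**
- Adjustments per DGF day: 5.1 to 5.7% rejections if timing is even. If adjustments cluster early, a log-days offset rejects against Envarsus XR in 6 to 47%, because the shorter period holds a larger share of the busy early days.
- Fixed 14-day count: ratio 1.00, 4 to 6%. If the adjustment rate halves once dialysis stops, 6 to 24%; if it falls to a quarter, 7 to 46%.
- Trough coefficient of variation, days 1 to 14, with equal true CV of 0.30 and troughs every 2 or 3 days on dialysis then weekly (assumed): 5.0 to 6.7%. This check does not model drift during conversion or the effect of deliberate dose changes.

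**The case against.** The endpoint as worded asks how many adjustments were needed during DGF. If DGF is shorter, that total really is lower, and it is a legitimate measure of burden. This stands. A reader might take the 35 to 73% as the false-positive rate of the endpoint; it is not. It is the rate at which the total would mislead if read as evidence of level stability, and only if the full effect on duration is real.

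Four further readings are tempting and go beyond the text.
- *Section 9.2 rules out a rate.* It does not; a per-day rate could be tested by either listed method. The gap is that none is specified.
- *The end of counting is undefined.* The label in Section 5.1.1 gives the period a natural reading, first to last dialysis. Sections 6 and 8.2.3 place recovery later, so the wording should be tied down, but this is an ambiguity and not a void.
- *The count is the trial's main result.* Only Section 9.3 says so. Section 4 makes early recovery the primary objective, Section 5.1.1 makes duration the primary endpoint, and Section 9.1 sizes the trial on it.
- *Data after recovery are certainly new follow-up.* The 3-month visits in Sections 8.1 and 8.2 may already cover them.

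It can also be said that fewer adjustments may themselves lead to earlier recovery, as Section 3.2 proposes. That is possible, but a raw total cannot separate it from shorter counting time.

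**Conclusion.** The point holds for interpretation. A lower Envarsus XR total during DGF is not by itself evidence of steadier levels, and no endpoint or analysis measures the secondary objective directly. The second half rests on the text alone.

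The size of the first half depends on assumptions. With identical, evenly spread adjustment behaviour and the full planned effect, the ratio is 0.72 and a Wilcoxon test rejects in about 35 to 73% of trials. The problem shrinks with a smaller effect on duration and can vanish if adjustments cluster early and counting runs to recovery. Where practice falls in that range is unknown. Because at the full effect these results almost always come with a significant DGF duration, the likely harm is a wrong account of mechanism in a trial already positive on its primary endpoint. The duration comparison itself is unaffected. This should be changed, with moderate confidence in the size.

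**What to change.** (a) Add within-patient trough variability (for example the coefficient of variation) over a fixed common window after randomisation, such as days 1 to 14, by assigned arm, from troughs already drawn, as the measure of the Section 4 secondary objective. Add two sensitivity analyses: one leaving out the Envarsus XR conversion week (Section 7.1 puts steady state at about 7 days), with the same days dropped in both arms, and one without troughs drawn after a post-study product switch. Note in the plan that early recovery and switching may differ by arm.

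(b) Keep the total during DGF as a descriptive result. State that it runs over the first-to-last-dialysis interval of Section 5.1.1, or name another end. Report a fixed-window count as supportive only, because it still rejects in up to about 45% of trials if adjustments drop sharply once dialysis stops. Do not rely on a simple per-DGF-day offset.

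(c) Reconcile Section 9.3 with Sections 4, 5.1.1, 5.1.2 and 9.1, so that DGF duration is the primary analysis and dose adjustment the secondary.

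Cost: endpoint wording, and chart review to day 14 for patients who recover sooner. Under the planning figures (duration under 7 days, plus 7) that is 15% of control patients, about 7 of 50, and 41% of Envarsus XR patients, about 20 of 50 (31%, about 16, if the SD is 5.04). Sections 6 and 8.2.3, which end participation at recovery, must be reconciled with the 3-month visits and participation in Sections 8.1 and 8.2 to confirm whether these data are already covered. Some patients will have few troughs, most of all once the conversion week is left out. Titration guidance in Section 7.1 also differs by arm, with an effect of unknown size on either measure. No dosing rule changes.

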5.1.3. Primary Safety Endpoints

Primary safety endpoints include: infections, malignancies, hematological complications including leukopenia, anemia, and thrombocytopenia, cardiovascular complications and events, neuropathy, tremors, gastrointestinal symptoms, uncontrolled hypertension, serious electrolytes abnormalities and immunosuppression-related adverse effects.

6. Study Subjects – Enrollment and Withdrawal

- A total of 100 subjects (50 subjects in each arm) with the diagnosis of DGF will be enrolled over a period of 2 years.
- DGF is defined as the need for a dialysis within the first week of transplant. Once potential DGF patients are identified, the transplant nephrology team will be consulted and the transplant nephrology provider will perform initial evaluation of a patient, discussion with the patient about his/her interest in participating in the research study and inform the research coordinator.
- Subjects will participate in the study until the recovery of DGF as documented by the provider as “discharged from the DGF clinic” or no need for dialysis for more than one week (7 days).
- Subject would be followed for maximum of 3 months. If they still need dialysis beyond 3 months, will be declared as primary dysfunction and will disqualify from the study.

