3.5. Potential Risk and Benefits to Subjects

3.5.1. Known Potential Risks

Immunosuppressants, including extended release Envarsus XR, increase the risk of developing lymphomas and other malignancies, particularly of the skin. Other risks include, an increased risk of developing bacterial, viral, fungal, and protozoal infections, including opportunistic infections. Medication errors, including substitution and dispensing errors, between tacrolimus immediate-release products and tacrolimus extended-release products were reported outside the U.S. This led to serious adverse reactions, including graft rejection, or other adverse reactions due to under- or over-exposure to tacrolimus. Envarsus XR caused new onset diabetes after transplant (NODAT) in kidney transplant patients, which may be reversible in some patients. African-American and Hispanic kidney transplant patients are at an increased risk of NODAT. Envarsus XR, like other CNIs, can cause acute or chronic nephrotoxicity, may cause a spectrum of neurotoxicities. Other risks includes, hyperkalemia, rise in creatinine, electrolytes disturbance, hypertension, QT prolongation, drug interaction with CYP3A inducers and inhibitors. Live attenuated vaccines during treatment with Envarsus XR is contraindicated. Other post marketing experience includes- blood and lymphatic system disorders, ear disorders, eye disorders, gastrointestinal

disorders, hepatobiliary disorders, hypersensitivity reactions, immune system disorders, metabolic and nutrition disorders, musculoskeletal and connective tissue disorders, neoplasm, nervous system disorders, renal and urinary disorders, respiratory, thoracic and mediastinal disorders and skin and subcutaneous disorders. When comparing Envarsus XR with immediate release tacrolimus, potential risks were almost similar between the two groups.

Refer to the FDA approved package insert for Envarsus XR in Appendix 1.

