10.4. Records Retention

Study records will be retained for a minimum of 7 years after study completion per the UW Madison policy and IRB guidance: <https://kb.wisc.edu/sbsedirbs/page.php?id=42378>. These documents should be retained for a longer period if required by an agreement with the sponsor. In such an instance, it is the responsibility of the sponsor to inform the investigator/institution as to when these documents no longer need to be retained.

11. Assessment of Safety

The investigator is responsible for monitoring the safety of subjects who have enrolled in the study. For this study, adverse events will be solicited from subjects to identify an occurrence or worsening of an unintended sign or symptom,

related to the ingestion of the study drug as per standard of care. The clinical team will ask subjects in each visit if they experienced any new medical related signs or symptoms since taking the study drug. Subjects will be asked about any adverse events they may have experienced. Only the adverse events considered related (possibly, probably or definitely) to the ingestion of the study drug will be entered into and managed in the data management system.

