11.1. Specifications of Safety Parameters

The risks to subjects in this trial will be minimized by compliance with eligibility criteria, clinical monitoring, adherence to protocol contraception requirements and investigator guidance regarding specific safety areas. The specific safety areas that will be closely monitored in this subject population are; thrombocytopenia, diarrhea, fatigue, nausea, vomiting, rash, risk of reactivation of viral infection, neutropenia, fluid deficit, uncontrolled hypertension, posterior reversible encephalopathy syndrome (PRES).

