11.1.1. Definition of Adverse Events (AE)

Adverse event (AE) means any untoward medical occurrence in a patient or subject administered a pharmaceutical product; the untoward medical occurrence does not necessarily have a causal relationship with this treatment. An AE can therefore be any unfavorable and unintended sign, symptom, or disease temporally associated with the use of a medicinal (investigational) product whether or not it is related to the medicinal product. This includes any newly occurring event, or a previous condition that has increased in severity or frequency since the administration of study drug. AEs will be assessed at study visits and during the final follow-up study visit. Only the adverse events considered related (possibly, probably or definitely) to the ingestion of the study drug will be entered into and managed in the data management system

For the purposes of this study, baseline symptoms will be collected prior to the administration of study intervention. Only those symptoms identified as new or worsened compared to the baseline assessment will be recorded as an AE. In addition, only those abnormal laboratory values or physical examination assessments that are considered clinically significant will be recorded in the study documents. [Pain and hematoma at transplant incision site will not be considered an AE.](#)

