11.4.4. Events of special interest

The safety data that will be reviewed includes the number and seriousness of infections, malignancies, hematological complications including leucopenia, anemia, and thrombocytopenia, cardiovascular complications and events, neurological symptoms, gastrointestinal symptoms, and immunosuppression-related adverse effects

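### Four sections enter only adverse events judged related to the study drug, while 11.3 requires all of them; in this unblinded trial non-serious AE counts may be too low and may differ by arm through attribution

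*Combined protocol and SAP*

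**What the plan says.** **Safety outcomes.** Section 5.1.3 gives an open list of primary safety endpoints that closes with "neuropathy, tremors, gastrointestinal symptoms, uncontrolled hypertension, serious electrolytes abnormalities and immunosuppression-related adverse effects". Section 11.4.4 has a similar list, ending "cardiovascular complications and events, neurological symptoms, gastrointestinal symptoms, and immunosuppression-related adverse effects". Section 11.1 names areas for close monitoring: "thrombocytopenia, diarrhea, fatigue, nausea, vomiting, rash, risk of reactivation of viral infection, neutropenia, fluid deficit, uncontrolled hypertension, posterior reversible encephalopathy syndrome (PRES").

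**Entry rule.** The opening of section 11 states: "Only the adverse events considered related (possibly, probably or definitely) to the ingestion of the study drug will be entered into" the data management system. Sections 11.1.1, 11.4.1 and 12.1 say the same. Section 11.4.1 adds that these entries are what the study team, the DMC and the monitoring service can see.

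**Opposing rule.** Section 11.3 has all non-serious AEs captured on the CRF, lists the relationship to study product as one item to be recorded, and asks for all on-study AEs to be documented irrespective of relationship.

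**Known harms.** Section 3.5.1 says "Envarsus XR caused new onset diabetes after transplant (NODAT) in kidney transplant patients, which may be reversible in some patients". It also says "Envarsus XR, like other CNIs, can cause acute or chronic nephrotoxicity", and concludes "When comparing Envarsus XR with immediate release tacrolimus, potential risks were almost similar between the two groups".

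**Blinding.** Section 7.4 states that the trial is unblinded.

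**The concern.** A safety comparison between arms needs events counted the same way in each. A rule that admits only events judged related makes each count the product of two things: how often the event happened, and how often a clinician who knows the treatment attributed it to the drug. The second factor need not be equal across arms, least of all when the term study drug may be read as naming only one of them.

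At stake is the non-serious AE summary by arm, for the DMC during the trial and for the report afterwards. A harm could look rarer than it is, or more common in one arm than the other, with no true difference.

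**Working it through.** The plan states no AE rate, attribution rate or safety precision, so there is no figure of its own to reproduce. The check is mainly a comparison of the texts.

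**1. Do the rules conflict?** On their face, yes. Sections 11, 11.1.1, 11.4.1 and 12.1 use relatedness as a condition of entry. Section 11.3 treats it as an attribute of an event that is recorded anyway.

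**2. Can they be reconciled by layer?** Section 10.2.2 describes CRFs completed in ink, and 10.2.3 describes direct electronic entry. One could let 11.3 govern the CRF and 11.4.1 the database. But 11.4.1 makes the filtered entries the material for cumulative review, 11.6 draws the DMC reports from OnCore and REDCap, and 10.2.5 makes REDCap the final repository. Under this reading the unfiltered events exist on the CRFs, yet the reviewed data are still the filtered set.

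**3. Does the filter treat the arms alike?** The text does not settle it.

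| Use of the term | Where |
|---|---|
| Envarsus XR, as opposed to the standard-of-care drug | Study Summary; 6.7.2; 6.7.3 |
| Broader, or both formulations | 6.3 (plural, study drugs); section 7 (both arms under Study Agent); Table 1 in 8.1 (dose adjustment of either drug) |

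**4. Is attribution a real judgement?** Often. New-onset diabetes is a useful example: 3.5.1 attributes it to Envarsus XR, but 7.3 allows steroids, a competing cause. Two clinicians could reasonably disagree, and each knows the arm.

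**5. Which events are affected?** Mainly non-serious ones. Section 11.4.2 has an SAE form sent to the DMC as soon as possible, with no relatedness limit in that sentence, and under 11.6 the DMC co-chairs review reported SAEs.

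**6. Illustration of size (all rates assumed).** Let p be a true event rate that is equal in both arms, and cE and cS the shares of cases entered in the Envarsus XR and standard-of-care arms.

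- Recorded rate = p × c.
- False difference = p × (cE − cS).

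With c anywhere from 40% to 80% in each arm:

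| True rate p | True cases among 50 (9.1) | Recorded rate | False difference, Envarsus XR minus control |
|---|---|---|---|
| 10% | 5 | 4-8% | −4 to +4 points |
| 20% | 10 | 8-16% | −8 to +8 points |
| 30% | 15 | 12-24% | −12 to +12 points |

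At p = 20%:

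- cE = 80%, cS = 50%: 10 × 0.8 = 8 cases against 10 × 0.5 = 5, a false difference of 0.20 × 0.30 = 6 points.
- cE = cS = 80%: 8 cases against 8. There is no false difference, but one case in five is lost in each arm.
- Limiting case, control-arm events never entered (cS = 0, cE = 80%): 0.20 × 0.80 = 16 points.

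Nothing in the documents says which of these would occur.

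**The case against.** **The loss may be small.** This stands. Under 11.2.2 an event is possibly related on some evidence, such as plausible timing. Many events would pass that bar in either arm.

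**The rules may sit at different layers.** This stands in part. If 11.3 governs the CRF, unfiltered events could be recovered later. It does not help the DMC or the study team while they work from the filtered set.

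**The data and safety monitoring plan may resolve it.** Section 11.4 says that plan will cover AE reporting to the DMC. It is Appendix 3 and was not available, so this cannot be ruled out. The protocol text would still contradict itself.

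**Stronger readings that a reader might infer, and that the documents do not support:**

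- *New-onset diabetes is left out of safety assessment.* No list names it. But 5.1.3 is an open list, and both it and 11.4.4 end in a catch-all for immunosuppression-related effects, which naturally covers it. It is unnamed, not excluded; nephrotoxicity is likewise unnamed.
- *A raised glucose can never become an AE.* Section 11.1.1 says "only those abnormal laboratory values or physical examination assessments that are considered clinically significant will be recorded in the study documents", while 11.4.1 says the PI will not judge the significance of laboratory results abstracted from the medical record. That is awkward, but the AE definition in 11.1.1 includes a disease, so a clinician's diagnosis of diabetes qualifies without a ruling on a laboratory value.
- *The DMC sees only filtered data.* The SAE route in 11.4.2 contradicts this, and 11.6 lets the DMC review source documents.
- *The rule favours one arm.* No direction can be derived, and 3.5.1 calls the two formulations' risks nearly alike.

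**Conclusion.** The concern holds for the recording rule. Sections 11, 11.1.1, 11.4.1 and 12.1 conflict with 11.3, so the plan is wrong as written. Applied literally, the related-only rule could make non-serious AE counts too low and could make them differ by arm through attribution in an unblinded trial. New-onset diabetes is an example of this, not a separate defect.

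The size and direction are unknown. The figures above rest on assumed event rates and assumed shares entered, and their range includes zero. The conclusion needs only the conflicting text, the absence of blinding and the unsettled meaning of study drug. Severity is minor: serious events have their own route, and the efficacy analysis does not depend on the rule.

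**What to change.** 1. In 11, 11.1.1, 11.4.1 and 12.1, replace the related-only entry rule with the 11.3 rule: enter all new or worsened AEs in both arms whatever the judged relationship, and keep relatedness as a recorded attribute.
2. State that study drug, and the 30-day period after the last dose in 11.3, cover both tacrolimus formulations, counted from the last on-study dose. The last clause is needed because 8.2.3 lets patients stay on the medication after leaving the study.
3. Report AEs by randomised arm, both all-cause and related.
4. Optional: name new-onset diabetes in 5.1.3, 11.1 and 11.4.4. A separate glucose or drug-start analysis is not recommended, because it would also pick up transient, steroid-related and pre-randomisation hyperglycaemia.

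The cost is wording in a few sections and more AE entry in a population with many events, although 11.3 already requires those events to be captured. No test or visit is added, and the efficacy endpoints and sample size do not change.
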